### **Vulnerable Populations**

N/A

### **Number of Participants**

Up to 50 participants will be recruited for the pilot test.

### **Study Timeline**

The overall project has a 12-month timeline.

### **Participants and Recruitment**

This project, located at Georgia State University (GSU), will draw on multiple sources to recruit the targeted informal care partners of persons living with moderate dementia into the study. We will recruit a sample of informal care partners of community-dwelling persons living with moderate dementia (4 or 5 on a 7-point dementia-staging scale) from Emory's Integrative Memory Care Clinic (IMCC). Located in Atlanta, GA, the IMCC provides primary care and is a one-stop health-care site for over 600 persons living with dementia. A support letter from [name], the clinic's Clinical Director, accompanies this application and outlines her commitment to assisting with the study, including designating an IMCC staff member as a study point person to help promote the study. This point person will promote the study to patients' informal care partners and share study information with potential participants. We will advertise the study and solicit volunteers through flyers posted and distributed in the clinic, shared in their newsletter, and sent via email to patients and their care partners. Informal care partners who are interested in potentially participating will be invited to contact GSU researchers by phone or email to obtain further details. The flyer contains contact information and a QR code. Those who reach out to the study team and remain interested after learning about the study will be screened over the phone to ensure they meet study criteria. Individuals who meet the criteria and who wish to volunteer will be

enrolled on an ongoing basis. Pilot testing will begin with the first group once we have recruited at least 8 participants. Research staff will clearly explain the requirements of the study prior to enrollment, obtain several contact avenues (phone numbers, email), and will work with participants as we schedule training sessions to identify days of the week/times of day that might be most convenient. If necessary, we are unable to recruit a sample of 40 participants through the IMCC, we will submit an IRB protocol amendment to expand our recruitment plan through other organizations and sites. At the recommendation of the advisory team (Aim 1) and ongoing recruitment feedback, we will expand recruitment to allow the flyers and newsletter information to be shared through by advisory team members, researchers, and participants, including snowball sampling. In the process of recruiting potential participants are asking if they may share the information with their peers. We also realize that flyers are posted and electronic communications are sent, they can be shared with others. We wish to include persons not directly recruited through the Emory's memory care clinic but who fit study criteria. In order to further expand recruitment, we wish to advertise on social media through the Gerontology Institute social media accounts with links to a webpage about the project hosted on the Gerontology Institute website. The website will include information from the recruitment flyer.

### **Inclusion Criteria**

Eligible participants will be: 1) 18-years or older; 2) actively engaged in the care of community-dwelling persons living with moderate dementia (4 or 5 on a 7-point dementia-staging scale) who is not likely to be institutionalized within the next 6 months; 3) able to attend at least 3 of the 4 in-person sessions. Participants also will need to be able to read, write, and communicate in English. Screening will take place over the phone when potential participants reach out to the study team and express interest in the study.

### **Participant Compensation**

Each participant will be given \$75.00 per in-person session to offset any care or travel costs and a total of \$375.00 per person for those who attend all five in-person sessions.

### **Benefits & Risks**

Study participants may benefit by having opportunities throughout the training to share their experiences and perspectives with others. In past, we have found that research participants enjoy the opportunity to talk about their experiences. The group-based interactions also will provide a social outlet, which they may find enjoyable. We anticipate that the training they receive will give them new skills and techniques to use as they perform their care roles. Ideally, these skills, including an ability to "be in the moment," may enhance their self-perceived caregiver mastery and possibly their self-

reported burden, anxiety, depression, perceptions of care recipients' behavioral expressions and associated care-partner distress and quality of life. We will not state to participants that taking part in the training program will be beneficial to them, although we believe and are hopeful that it will. We also will acknowledge that study participation may eventually contribute to the well-being of other informal care partners. If this intervention shows signs of efficacy, we will pursue additional funding to conduct further tests and ideally scale up the intervention in size and scope, including for instance, training for formal care partners and others. Improv training has the potential to improve dementia care experiences for all types of care partners, health care workers, and others who engage with persons living with dementia in all types of settings.

Participating in this study will involve taking part in an in-person group training program for informal care partners of persons living with moderate dementia. There is a potential risk for discomfort and emotional distress when study participants discuss their caregiving experiences. Taking part in the research surveys also may prove uncomfortable when reflecting on their experiences and on their own and their care recipient's well-being. Another potential for minimal discomfort and emotional distress could arise when participants attempt their homework assignments, which involve applying communication strategies from training sessions in the context of caring for their loved one with dementia. There also is minimal risk associated with potential breach of privacy and confidentiality. Breach of privacy could occur given the group nature of the intervention and our inability to control what participants will share outside of the group. Meanwhile, although there is virtually no risk to the confidentiality of the research data, it is among the potential risks.

### **Participant Data**

Upon enrollment, each participant will be assigned a unique numeric participant code, which will appear on the self-administered questionnaires. Members of the research team will distribute questionnaires to participants during in-person sessions at baseline, upon program completion, and 3-months post baseline. These pen & paper self-administered questionnaires will be filled out by participants in a dedicated meeting space within Emory's Integrated Memory Care clinic (see 8.0). Completed surveys will be transported to Georgia State University by a designated member of the research team. All hard copies of participant surveys and signed consent forms, as well as any other relevant project data and documents, will be kept in a locked cabinet in PI [name]'s locked office, which is located within a locked research suite. All quantitative survey data will be entered into GSU's REDCap data management system.

Researcher-generated fieldnotes and memos based on their observations of the in-person sessions will be created in Word files in the project's secure storage folder and stored electronically as described below.

These notes will capture what is happening in the training sessions, including what is being said and done and by whom. We will use participants' initials, rather than their name, in these notes. Only the PI and designated project staff will have access to individually identifiable private information. Participant tracking information will be kept on files that do not identify the project or the respondent and these too will be handled with the utmost confidentiality. The file linking the ID numbers to subjects' identities will be kept in [name] password-protected Georgia State University's Dropbox for Business a secure cloud-based server. All electronic study records, including our quantitative and qualitative databases, and all digital audio recordings, will be stored on a secure, remote, password-protected cloud server, Dropbox for Business. The project will be assigned its own folder accessible only to active research team members with IRB approval. The folder is maintained and monitored by Georgia State University's Technology Services. This storage solution meets NIH's requirements for secure storage. To protect participant privacy, the document linking participant names and study numbers will be destroyed one year after the study ends. We will remove any identifying features and use pseudonyms to protect the anonymity if our qualitative data are shared outside of the research team or used for dissemination purposes. When we present or publish the results of this study, we will not use information that may identify participants. If researchers inadvertently collect identifiable data that are not specified in our protocol, researchers will de-identify the relevant data immediately upon discovery.

### **Data Analysis Plan**

Descriptive statistics will be calculated for all demographics and instrument scores at baseline, completion, and three months after baseline. Internal reliability will be assessed using Cronbach's alpha at baseline. Missingness will be assessed and corrective measures used as appropriate (multiple imputation). Repeated measures analysis of variance will be used with dependent variables across the three time points. Error rate adjustments (Bonferroni or Dunn-Sidak tests) will be made due to the implementation of multiple comparisons across dependent variables. Effect sizes will also be computed and assessed for clinical significance. The percentages of caregivers whose scores improve or decline from baseline to completion and post-completion assessments will be calculated. IBM SPSS for Windows, version 24.0 will be used to perform computations.

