## **Brief Description of Project Design**

- Phase 1 involves refining the training program, "Improving Care through Improv" (Aim 1).
- Phase 2 involves piloting the training program with 40 adult informal care partners of person with moderate dementia to test its effect on self-perceived caregiving mastery through a no-control, pre-post design single-group trial with three time points: baseline; immediately upon completion, and 3-months post baseline (Aim2). The intervention will be delivered to up to 5 groups of 8 to 12 participants each. All groups will be exposed to the same in-person training during weekly 2-hour sessions held over a 4-week period. At 3-months post baseline, there will be a 90-minute in-person session to allow for completion of the assessment and to obtain participant feedback.

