## **Procedures/Human Subjects Involvement**

Study participants will be exposed to the same in-person group training delivered by study personnel during weekly 2-hour sessions held over a 4-week period. In addition to the four in-person training sessions, participants will be invited to attend a final one-and-a-half hour in-person group meeting, which will involve completion of the 3-month post baseline assessment and invite feedback on the overall intervention experience through

open-ended questions. Participants will complete a self-administered pen and paper survey at all three study time points: baseline; upon training completion; and 3-months post baseline. At baseline, we will collect care partners' demographic details (e.g., age, gender, race, ethnicity, employment status, education, urban/suburban/rural status, relationship to care recipient), and key information pertaining to their caregiving history, experiences, and care recipient.

At all three time points, participants will be asked to complete measures to assess: caregiver mastery, self-perceived stress, anxiety, caregiver burden, and perceived changes in care recipients' behavioral expressions and with associated care partner distress. We also will ask participants to assess their care recipients' quality of life. Participants will complete these self-administered surveys in person with researchers present to answer any questions. The surveys collected at baseline and upon training completion will be distributed and completed at the first and fourth training sessions, respectively.

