Three months post baseline, we will reconvene the group and distribute the final survey and invite feedback on the feasibility and accessibility of the intervention. This session will be 90 minutes long. Researchers will take detailed fieldnotes to capture the content of the group discussion, especially their feedback on their intervention experiences. Participants will take part in the training program, "Improving Care through Improv." The training builds care partner skills cumulatively over a series of four classes, each with a separate focus: (1) Yes, and....: Actively listening and observing and offering and accepting interactions; (2) Being in the moment: Meeting people where they are and committing to what is happening; (3) How to collaborate: Give, take, and making your partner look good; (4) Giving up control: Accepting failure, pivoting, being flexible, leaning into uncertainty, and expecting the unexpected. All classes are highly interactive and invite informal caregiver to engage with the instructors and one another. The first class (Yes, and...), will begin with introductions, which will allow instructors and participants to gain familiarity and comfort with one another and share their care situations and experiences. The subsequent three classes (Being in the moment; How to collaborate; and Giving up control), will begin by inviting participants to reflect on the previous week, including care experiences and any attempts to use improv with their care recipients. Each week, an icebreaker exercise will follow opening discussions. Next, the instructors will provide an overview of the weekly topic and illustrate relevant skills through demonstration. Then, they will introduce and teach relevant improv exercises, which will allow participants to model and apply skills, first with the trainers and then amongst other caregivers. Feedback and coaching will follow each exercise. The final 20 minutes of each 2-hour class will be devoted to review, reflection, and group discussion, including how improv skills could be applied to their caregiving

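### Caregiving mastery is the only outcome the pilot is said to test, yet it shares a Bonferroni or Dunn-Sidak correction with every other score, which costs power if the gain is small or moderate

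*Combined protocol and SAP*

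**What the plan says.** The Brief Description of Project Design gives the purpose of the pilot as "to test its effect on self-perceived caregiving mastery through a no-control, pre-post design single-group trial", with assessments at baseline, completion and 3 months. It names no other outcome for that test, and the word primary is not used.

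Procedures/Human Subjects Involvement lists what is measured at every time point: "caregiver mastery, self-perceived stress, anxiety, caregiver burden, and perceived changes in care recipients' behavioral expressions", together with the care partner's related distress. It adds the care recipient's quality of life. That makes six scores if behaviours and distress form one score, and seven if they are separate.

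The Data Analysis Plan applies one repeated measures analysis of variance approach to all dependent variables and continues: "Error rate adjustments (Bonferroni or Dunn-Sidak tests) will be made due to the implementation of multiple comparisons across dependent variables". It gives no overall significance level, number of comparisons, testing order or exemption for mastery, and it names no formal contrasts between time points. It does promise descriptive statistics at each time, effect sizes, and percentages improving or declining.

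**The concern.** The design statement and the analysis plan do not match. One sets out to test a single outcome; the other spreads the error rate evenly over everything measured. The outcome the pilot exists to test therefore pays for scales that the design statement does not mention. If the true gain in mastery is small or moderate, its formal test is weaker than it needs to be.

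Two smaller gaps go with this. The threshold for mastery depends on a count the plan never fixes: behaviours and distress may be one score or two, and depression appears among the hoped-for benefits in Benefits & Risks but not in the list of measures. Also, a significant F test over three time points does not by itself show whether mastery rose, or when.

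**Working it through.** The documents give no significance level, effect size, SD, correlation or power, so there is no stated figure to reproduce. Everything marked *assumed* below is an input supplied for illustration.

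**Inputs**
- Planned size 40 (Brief Description of Project Design), with a ceiling given under Number of Participants: "Up to 50 participants will be recruited for the pilot test". A size of 32 is *assumed*, to show 20% attrition from 40.
- Number of scores k = 6 or 7, counted from Procedures/Human Subjects Involvement.
- Overall two-sided level 0.05 (*assumed*).
- Correlation between time points ρ = 0.6, equal for all pairs (*assumed*).
- Mean mastery at baseline, completion and 3 months, in SD of the score (*assumed*): sustained 0/0.4/0.4; delayed 0/0.2/0.4. A fading gain, 0/0.4/0.2, gives the same F test power as the delayed one.

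**Step 1: threshold for mastery**
- Bonferroni: 0.05/6 = 0.00833; 0.05/7 = 0.00714.
- Dunn-Sidak: 1 − 0.95^(1/6) = 0.00851; 1 − 0.95^(1/7) = 0.00730.
- If depression is also scored (k = 8): 0.00625 and 0.00639.

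**Step 2: power of the planned F test**

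The test has 2 and 2(n − 1) degrees of freedom and noncentrality λ = n·Σ(mᵢ − m̄)²/(1 − ρ). For n = 40:
- Sustained: m̄ = 0.2667, Σ = 0.1067, λ = 40 × 0.1067/0.4 = 10.67.
- Delayed: m̄ = 0.2, Σ = 0.08, λ = 40 × 0.08/0.4 = 8.0.

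| n | Sustained, 0.05 | Sustained, 0.05/7 | Delayed, 0.05 | Delayed, 0.05/7 |
|---|---|---|---|---|
| 32 | 73% | 43% | 59% | 30% |
| 40 | 83% | 57% | 70% | 41% |
| 50 | 91% | 72% | 80% | 54% |

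With six scores instead of seven, the adjusted figures at n = 40 are 59% (sustained) and 43% (delayed).

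**Step 3: how far this depends on the assumptions** (n = 40, sustained gain, 0.05 versus 0.05/7)
- Gain 0.3 SD: 57% versus 28%. Gain 0.5: 96% versus 83%. Gain 0.6: 99.4% versus 95.8%. Gain 0.7: 99.9% versus 99.4%.
- Correlation 0.4, gain 0.4: 65% versus 35%. Correlation 0.8: 99% versus 93%.
- Paired test in SD of change: 69% versus 39% at 0.4, and 87% versus 63% at 0.5. A gain of 0.4 SD of the score at ρ = 0.6 equals 0.4/√(2 × 0.4) = 0.447 SD of change.

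**Step 4: training groups**

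The plan states: "The intervention will be delivered to up to 5 groups of 8 to 12 participants each". The planned F test has no group term. It was simulated with 5 groups of 8 and an *assumed* intraclass correlation of 0.05 in the within-person residuals. Power hardly moves: 81% versus 59% sustained, 70% versus 45% delayed. The false-positive rate does move: about 11% at nominal 0.05, and about 2.3% to 2.4% at nominal 0.05/7. At an intraclass correlation of 0.02 it is about 7% at nominal 0.05.

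**Step 5: which time comparison should carry the claim**

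A delayed gain is plausible. On timing, the plan says "The surveys collected at baseline and upon training completion will be distributed and completed at the first and fourth training sessions, respectively", and on content, "The training builds care partner skills cumulatively over a series of four classes". With the delayed pattern (n = 40, ρ = 0.6), the baseline-to-completion contrast alone has 28% power at 0.05, against 70% for the F test.

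**The case against.** The strongest reply is that this is a choice and not an error. Adjusting across all scales is valid and conservative, mastery is never called primary, and the second aim is feasibility, acceptability and preliminary efficacy. No decision hangs on the p-value. Effect sizes are to be judged for clinical significance, and the test for going further is loose: "If this intervention shows signs of efficacy, we will pursue additional funding to conduct further tests". With no control group, a significant change could reflect time alone. The size of the loss rests wholly on assumed values. Direction and timing will be visible in the descriptive results even without formal contrasts.

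Most of this stands, and it limits the weight of the point. It does not remove the mismatch: the plan chose formal testing with error control, and that test should fit the outcome the design statement names.

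The reply is also right that testing mastery at a full 0.05 beside a separate 0.05 for the other scales would raise the overall bound from 5% to at most 10% (1 − 0.95² = 9.75% if independent). Testing the other scales only after mastery passes answers that.

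Three stronger readings are tempting and not supported:
- A reader might infer that the adjustment is wrong. It controls the error rate as intended; the issue is efficiency.
- A reader might infer that the pilot cannot detect a gain in mastery. The documents give no effect size, and for large gains the loss nearly vanishes.
- A reader might apply a design effect of 1 + 7 × 0.05 = 1.35 and conclude that grouping cuts the sustained-gain figures to 69% versus 40%. That is the power of a test corrected for grouping. The plan describes no such test; under its uncorrected one, grouping mainly inflates false positives.

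**Conclusion.** The point holds as one of efficiency and alignment, with modest priority. The analysis charges the one named efficacy outcome for five or six other scores. Under the assumptions above, sustained or delayed gains of 0.3 to 0.4 SD lose roughly 20 to 30 points of power at n = 32 to 50 and ρ = 0.6. The loss is about 13 points at a sustained 0.5 SD with n = 40, and 4 points or less from 0.6 SD upwards. The conclusion needs an overall level of 0.05 and the natural reading that the adjustment covers every dependent variable. Adding pairwise time comparisons to the same family would lower the threshold further.

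Every error rate quoted for the plan or for the fix holds only for independent participants. If members of a training group change alike, the planned test exceeds its nominal level whichever threshold is used.

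**What to change.** Amend the Data Analysis Plan as follows:

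1. State the overall level. Name mastery as the single primary efficacy outcome and test it first, by the planned repeated measures F test at 0.05, without adjustment for the other scales.
2. If that test is significant, report the baseline-to-completion and baseline-to-3-months contrasts with direction and confidence intervals, adjusted for two comparisons. Do not rest the claim on baseline to completion alone.
3. List the other outcomes by name and number as secondary. Test them by Holm (or Holm-Sidak) in place of single-step Bonferroni (or Dunn-Sidak), formally only after mastery passes. Holm controls the same error rate as Bonferroni and is never less powerful. The bound over the mastery F test and the secondary scales then stays at 5%; the two contrasts carry their own adjustment.
4. Say that these levels assume independent participants and that the F test does not account for training group.

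The cost is a few sentences and no new data. If mastery does not pass, the other scales are descriptive only, and a secondary scale cannot become the headline efficacy result. Requiring an upward contrast after the F test costs 1 to 3 points of power at n = 40 (83% to 81% sustained, 70% to 67% delayed).

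### The multiplicity correction is valid but single-step; Holm's step-down procedure would never reject less than Bonferroni at the same family-wise error (optional efficiency gain)

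*Combined protocol and SAP*

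**What the plan says.** The Data Analysis Plan gives one sentence on multiplicity: "Error rate adjustments (Bonferroni or Dunn-Sidak tests) will be made due to the implementation of multiple comparisons across dependent variables". The tests being adjusted are described just before it: "Repeated measures analysis of variance will be used with dependent variables across the three time points". The choice between the two adjustments is left open, and the plan states neither an alpha level nor the number of tests in the family.

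The scores are listed under Procedures/Human Subjects Involvement: "caregiver mastery, self-perceived stress, anxiety, caregiver burden, and perceived changes in care recipients' behavioral expressions and with associated care partner distress". That section then adds: "We also will ask participants to assess their care recipients' quality of life". This makes six scores if behavioral expressions and the associated distress count as one scale, and seven if they count as two.

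The Brief Description of Project Design sets the size: "Phase 2 involves piloting the training program with 40 adult informal care partners". Number of Participants allows for up to 50. No power calculation is given.

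**The concern.** A single-step rule holds every score to the threshold that is needed only for the smallest p-value. Once one null hypothesis has been rejected, fewer remain to protect, and a step-down rule relaxes the threshold accordingly without raising the family-wise error rate. With about 40 participants, a scale that has really changed may miss 0.05/7 yet pass the threshold that a step-down rule would apply at its turn. Benefits & Risks says that signs of efficacy would lead to further funding and testing, so an avoidable non-significant result on a secondary scale could influence what is carried forward.

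**Working it through.** **Inputs from the documents.** Single-step Bonferroni or Dunn-Sidak; m = 6 or 7 scores; n = 40; repeated measures ANOVA over three time points. There is no stated power or threshold to reproduce.

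**Assumptions, not in the documents.** Family-wise two-sided alpha 0.05; m = 7 unless stated; shifts of 0.3 to 0.5 SD, present at both follow-ups; within-person correlation 0.5; between-scale correlation 0.3 or 0.6. With within-person correlation 0.5, the SD of change is SD × √(2 × (1 − 0.5)) = 1 SD, so shifts in SD of score and in SD of change are on the same footing below.

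**1. Thresholds.**
- Bonferroni, alpha/m: 0.05/7 = 0.00714; 0.05/6 = 0.00833.
- Dunn-Sidak, 1 − (1 − alpha)^(1/m): 1 − 0.95^(1/7) = 0.00730; 1 − 0.95^(1/6) = 0.00851.
- Holm, alpha/(m − i + 1) for the i-th smallest p-value, stopping at the first failure. For m = 7: 0.00714, 0.00833, 0.0100, 0.0125, 0.0167, 0.025, 0.05.

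**2. Ordering of the rules.** Holm's first threshold equals Bonferroni's and its later ones are larger, so every Bonferroni rejection is also a Holm rejection. This is exact and needs no simulation. Against Dunn-Sidak the ordering is not strict: with seven scales, a smallest p-value between 0.00714 and 0.00730 passes Dunn-Sidak and fails Holm. Step-down Sidak starts at 0.00730 and does dominate Dunn-Sidak.

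**3. Average power per truly changed scale.** Simulation of the planned ANOVA F test, m = 7, n = 40, between-scale correlation 0.3, 10,000 runs per row:

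| Scales that change | Bonferroni | Dunn-Sidak | Holm | Holm − Bonferroni |
|---|---|---|---|---|
| 1 of 7, 0.4 SD | 43.9% | 44.1% | 44.0% | 0.1 |
| 3 of 7, 0.4 SD | 44.2% | 44.4% | 46.4% | 2.2 |
| 7 of 7, 0.3 SD | 20.6% | 20.8% | 24.3% | 3.7 |
| 7 of 7, 0.4 SD | 44.7% | 44.9% | 54.6% | 9.9 |
| 7 of 7, 0.5 SD | 70.1% | 70.4% | 82.7% | 12.6 |

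At correlation 0.6 the gains for all seven are 5.2 points (20.4% to 25.6%), 9.5 (44.2% to 53.7%) and 10.3 (70.9% to 81.2%). If uncorrelated scales are also allowed, the all-seven range widens to about 2 to 14 points.

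**4. A simpler model as a cross-check.** One paired test per scale, n = 40, between-scale correlation 0.4, shift 0.5 SD. With four of seven changed, Bonferroni gives 62.7% and Holm 67.3% (4.6 points). With all seven, 63.5% and 75.8% (12.3 points). With all of six, 65.2% and 77.3% (12.1 points). With one of seven, 63.0% under both. The pattern does not depend on the choice of test.

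**5. What does not change.** With all seven scales shifted by 0.4 SD at correlation 0.3, the chance of at least one rejection is 92.0% under both Bonferroni and Holm (92.1% under Dunn-Sidak), because their first thresholds are the same.

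**6. Error control.** When no scale changes, Holm's family-wise error equals Bonferroni's: 4.75% at correlation 0.3 and 3.87% at 0.6. In the mixed cases at these two correlations (one or three scales changed), Holm's was at most 4.3%.

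**The case against.** The strongest reply is that the plan's choice is legitimate. Bonferroni and Dunn-Sidak control the error they are meant to control, and this is a pilot for feasibility, acceptability and preliminary efficacy. It also reports effect sizes and the percentages improving or declining, so its conclusions do not rest on adjusted significance alone. That stands, and it is why the point is optional.

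Four stronger readings are tempting, and none is supported.

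- **That Holm beats both named rules.** It strictly beats Bonferroni only. In the ANOVA simulations Dunn-Sidak rejected something Holm did not in up to 0.4% of trials. The reverse was far more common when many scales changed (42% of trials with all seven at 0.4 SD), so the advantage there is practical and not strict.
- **That correlation between the scales favors Holm.** Holm makes no use of correlation, and the documents report none.
- **That the plan gives up power for nothing.** Single-step rules come with matching simultaneous confidence intervals; Holm has no simple equivalent. The plan does not mention intervals, but it does intend to interpret effect sizes.
- **That the plan will miss real changes.** This needs several scales to change by amounts the documents do not state. The Brief Description of Project Design aims the pilot at one outcome: "to test its effect on self-perceived caregiving mastery through a no-control, pre-post design single-group trial with three time points". Benefits & Risks expresses only a qualified hope for the other scales. If mastery alone changes, Holm gains essentially nothing.

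It is also fair to say that the same sentence has a larger gap: the family is not listed and mastery is given no test of its own. Closing that gap might matter more for power. It is compatible with the change proposed here.

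**Conclusion.** The point holds as an efficiency improvement. The named rules are valid but less efficient than their step-down versions. That Holm never rejects less than Bonferroni at the same family-wise error is certain. The size of the gain is conditional on family-wise two-sided 0.05, n = 40, shifts of 0.3 to 0.5 SD and moderately correlated scales: about 0 points of average power per changed scale if one changes, about 2 to 5 if three or four of seven change, and about 4 to 13 if all change. None of these effect sizes or correlations comes from the documents, so the figures illustrate the gain and do not state this trial's power. Leaving the sentence as it stands would not make the analysis invalid.

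**What to change.** In the Data Analysis Plan, replace the bracketed Bonferroni or Dunn-Sidak wording with: Holm's step-down procedure (family-wise two-sided 0.05), applied to the repeated measures ANOVA p-values of the listed scales. List those scales, so that it is clear whether the family has six or seven members. Report Holm-adjusted p-values with effect sizes and 95% confidence intervals labelled as unadjusted. Make the change before the scores are analysed, since choosing among adjustments after seeing p-values would undermine the error control.

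The cost is one sentence and no new data; the adjusted values can be worked out by hand from the SPSS output. The small downside is that an unadjusted interval may exclude zero beside a non-significant adjusted p-value, which the label should make clear. Step-down Sidak would also serve and strictly improves on Dunn-Sidak, but the simulated difference from Holm is at most 0.4 points of average power, and Holm is valid under any dependence.
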